3.3 Secondary Objective(s) & Hypothesis(es)

(2) **Objective**: To determine safety and tolerability of pembrolizumab for patients with oral IEN

Hypothesis: Pembrolizumab will have similar or better toxicity profile as in patients with advanced cancers

(3) **Objective**: To determine the histologic and clinical response rates (in the subgroup of patients with clinically evident, measurable oral IEN lesions) to pembrolizumab

Hypothesis: Pembrolizumab will reverse histologic changes associated with oral IEN, and will reduce the size of clinically evident oral IEN lesions (i.e., leukoplakia and/or erythroplakia)

(4) **Objective**: To characterize the immune infiltrate in oral IEN lesions before and after treatment with pembrolizumab.

Hypothesis: Pembrolizumab will stimulate a specific, monoclonal / oligoclonal adaptive immune response

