4.2 Rationale

4.2.1 Rationale for the Trial and Selected Subject Population

Oral pre-malignant lesions, or intra-epithelial neoplasias (IEN), are in and of themselves markers of oral cancer risk. Clinically, they are often recognized as leukoplakia and/or erythroplakia. Histologically, they are often characterized as hyperplasia/hyperkeratosis, mild, moderate and/or severe dysplasia / carcinoma in situ. ¹

Despite extensive investigations, a drug that can be used as standard of care to treat oral IEN and/or to reduce cancer incidence in patients with oral IEN is yet to be developed.¹

The need for novel trial designs to successfully develop drugs for management oral IEN has recently been highlighted. ¹⁻³ This includes (a) the use of convergent trial designs, ⁴ (b) focus on high risk populations, ³ (c) identification of intermediary endpoints related to the biology of the agent used in earlier-stage trials that can inform subsequent larger-scale studies and novel strategies, ^{3,5} (d) reverse migration of active agents from use in advanced cancers settings to pre-malignant lesion settings. ⁶

Convergent trial designs recognize that IEN and early stage invasive cancers share common pathogenesis. Therefore, patients with oral IEN lesions and curatively treated (resected) oral cancers may exhibit similar, increased risk of developing a primary invasive oral cancer, a second primary tumor, or recurrence. This is especially true for molecularly defined, high risk subgroups. As such, modern trials can combine patients with high risk IEN that may or may not have had a prior history of oral cancer, in designs that converge prevention and adjuvant therapy to understand the molecular biology of candidate therapeutic agents and their ability to reduce subsequent cancer development. Specific to oral IEN, high risk groups can be molecularly defined as IEN exhibiting high risk LOH profiles (i.e., LOH positive group).

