5.8.1 Discontinuation of Study Therapy

Subjects must discontinue therapy for the following reasons:

- Withdrawal / discontinuation from study.
- Worsening oral lesions requiring discontinuation from study therapy, in the opinion of the treating physician
- Unacceptable adverse experiences as described in Section 5.2.1.2
- Intercurrent illness that prevents further administration of treatment
- Investigator's or patient's decision
- The subject has a confirmed positive serum pregnancy test
- Development of oral cancer
- The subject is lost to follow-up

For patients that develop oral cancer during the study or for patients that are lost to follow up, only the procedures described under "Lon-Term Follow-Up" in section 6.0 will be performed.

If possible, subjects that discontinue therapy before completing 4 cycles of treatment should remain on study and continue to undergo study procedures and follow-ups as described in Section 6.0.

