7.1.5 Tumor Biopsies/Archival Tissue Collection/Correlative Studies Blood and Oral Swabs

Biospecimens collected (including archival and newly obtained oral tissue, blood, oral swab, and invasive cancer specimens) will be used for LOH evaluation, evaluation of histological response to treatment (a secondary objective of the study), as well as correlative studies. As part of the study, a biospecimen repository will be created. The objective of this repository will be to provide material for future evaluations of other relevant biomarkers that may be associated with clinical outcomes. A written informed consent will be obtained from patients enrolled in this study so that these samples may be analyzed in the future for biomarkers not described in this protocol.

Because the population randomized on this study is considered high risk, oral biopsies performed at baseline, months 3 and 12 are considered standard of care for monitoring for histological progression and invasive cancer development.

Biospecimen collection and handling are described in the Appendix.

The correlative studies to be evaluated in the biospecimens include (but are not limited to):

- expression of PD-L1, PD-L2, B7-H3, B7-x/H4, PD-1, LAG-3, 2B4, BTLA, Tim3 in neoplastic cells, immune cells and epithelium
- expression of CD3, CD4, FoxP3, CD8, CD68, CD57, CD45RO in immune cells
- T cell receptor profiling by massive parallel sequencing, and/or T cell receptor expression assay (DTEA)
- whole exome sequencing to determine presence of neo-antigens
- oral microbiome characterization
- genomic analysis (including genome sequencing and SNP analysis)
- proteomic analysis
- phosphorylation status of multiple kinases (using antibody arrays when appropriate)

- non-coding-RNA and messenger-RNA levels, including the expression signatures interferon gamma, TCR signaling, expanded-immune, de novo.
- identification of sub-populations of T-cells (e.g. CD4+ helper T-cells, CD8+ cytotoxic T-cells, CD4+ CD25+ regulatory T-cells, FOXP3) and myeloid derived suppressor cells (CD19-, CD3-, CD14-, HLADR-, CD11b+, CD33+, CD45+) as well as immune phenotypic markers including ICOS/ICOSL; OX40/OX40-L; 41BB/41BB-L; PD-1/PD-L1 and PD-L2; CD69, and HLA-DR (activation markers that affect T cell function)
- Cytokine profiling
- Pembrolizumab serum levels and anti-pembrolizumab antibodies
- Other biomarkers that may emerge to be important related to the biology of oral IEN and/or pembrolizumab therapy

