8.1 STATISTICAL CONSIDERATIONS

8.2 Study design and sample size justifications

This randomized phase 2 trial focuses on the definitive primary endpoint of oral cancer-free survival, thus eliminating the limitations of utilizing intermediate endpoints for efficacy analysis. Unfortunately, clinical and/or histologic responses of IEN lesions to chemoprevention interventions only marginally correlate with long-term oral cancer-free survival, as demonstrated by larger-scale retinoid-based therapy trials. As such, the most appropriate way to accurately estimate activity of a candidate drug to manage oral IEN is to use oral cancer-free survival as an endpoint.

The advantages of selecting a molecularly-defined high risk group as the eligible population include: (1) increased number of expected events, thus reducing the sample size; (2) avoidance of exposure of low-risk individuals to the drug, who are unlikely to develop oral cancer and therefore, unlikely to benefit from prevention interventions; (3) improvement of benefit/risk rations and benefit/cost ratios, justifying further use of the drug if positive effects are identified.

The proposed study will be an open-label, observation-controlled randomized study to evaluate the effect of pembrolizumab in a high-risk group of oral IEN patients. There will be two categories of high-risk patients in this study: (a) loss of heterozygosity (LOH) at 3p14 and/or 9p21 in the oral IEN of patients with a history of curatively treated oral cancer and (b) LOH at 3p14 and/or 9p21 plus at one other chromosomal region in the IEN of patients with no oral cancer history.

Study Duration: The trial period is 7 years with 4 years of accrual and 3 additional years of follow-up after last patient's enrollment.

Study Endpoints: The primary endpoint is oral cancer-free survival in patients receiving pembrolizumab as compared with the observation group. Multiple secondary and/or exploratory endpoints will be assessed as outlined in Section 3.2 and 3.3.

Treatment Groups: This is a 2-arm open-label Phase II single-center trial of pembrolizumab versus observation in patients with oral IEN. The trial will randomize 104 patients (1:1)to receive pembrolizumab versus observation.

Sample Size Justification

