10.4 Criteria for evaluating clinical and histologic responses

Definitions of clinical response (to be recorded at months 3 and 12):

- disease progression: increase of at least 25% in the sum of the product of the diameters of all visible lesions compared to baseline, and/or development of new lesions compared to baseline
- partial response: decrease of at least 50% in the sum of the product of the diameters of all visible lesions compared to baseline
- complete response: resolution of all baseline visible lesions
- stable disease: all other cases

Proprietary Information of MD Anderson Document Protect: JMK 2479, 2016 NCT02882282

Definitions of histological response (to be recorded at months 3 and 12):

- yes: resolution of baseline hyperplasia / hyperkeratosis / parakeratosis, resolution of baseline dysplasia, or improvement of baseline dysplasia by at least one grade
- no: all other cases

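### Read literally, the histologic response rule counts resolved keratosis or hyperplasia as a response even when the same biopsy shows new or higher-grade dysplasia or invasive cancer

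*Combined protocol and SAP*

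**What the plan says.** Histologic response is a secondary endpoint. Section 3.3 gives its hypothesis: "Pembrolizumab will reverse histologic changes associated with oral IEN". Section 10.4 defines it for months 3 and 12 in two lines. A patient is a responder under "yes: resolution of baseline hyperplasia / hyperkeratosis / parakeratosis, resolution of baseline dysplasia, or improvement of baseline dysplasia by at least one grade", and the only other category is "no: all other cases". There is no histologic progression category.

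The clinical response criteria in the same section are built differently. They define progression, and they count growth "and/or development of new lesions compared to baseline".

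Section 7.1.5 states what the biopsies are for: "oral biopsies performed at baseline, months 3 and 12 are considered standard of care for monitoring for histological progression and invasive cancer development". Section 4.2.1 describes the histology of these lesions: "Histologically, they are often characterized as hyperplasia/hyperkeratosis, mild, moderate and/or severe dysplasia / carcinoma in situ". Section 8.3 (Statistical Analysis Plan) adds no rule for scoring histologic response. Section 4.2.3.1 gives one reason for keeping the response endpoints: their association with long-term oral cancer-free survival can be studied.

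**The concern.** The three routes to a response are alternatives, and the first concerns only keratosis or hyperplasia. Loss of that feature is enough by itself. For example, a patient with hyperkeratosis and mild dysplasia at baseline, and severe dysplasia without hyperkeratosis at month 12, meets the definition. So does a patient with hyperplasia alone at baseline whose follow-up biopsy has lost the hyperplasia but shows dysplasia.

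Two things are at stake. First, each arm's secondary response rate can include patients who are histologically worse. Second, section 8.3 counts histologically confirmed oral cancer as a primary-endpoint event, so one month 3 or month 12 biopsy could make a patient both a histologic responder and an event. That would blur the association foreseen in section 4.2.3.1.

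**Working it through.** The plan states no expected rate, power or threshold for histologic response, so there is no figure to reproduce. The check applies the rule literally to every possible pattern.

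**Inputs.** From sections 4.2.1 and 10.4: keratosis/hyperplasia (K) absent or present; dysplasia none, mild, moderate or severe (including carcinoma in situ). At follow-up, invasive cancer is a further possibility and is not counted as resolved or improved dysplasia.

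**Number of patterns.** Baseline: 2 × 4 − 1 = 7 states, leaving out normal epithelium. Follow-up: 2 × 5 = 10 states. Total: 7 × 10 = 70.

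**Scoring.** A pattern scores yes if K was present and is now absent, or if dysplasia has resolved, or if dysplasia has fallen by at least one grade. It is worse than baseline if the dysplasia grade is higher or invasive cancer is present.

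| Baseline | Patterns | Score yes | Of these, worse than baseline |
|---|---|---|---|
| No K, mild dysplasia | 10 | 2 | 0 |
| No K, moderate | 10 | 4 | 0 |
| No K, severe | 10 | 6 | 0 |
| K, no dysplasia | 10 | 5 | 4 |
| K, mild | 10 | 6 | 3 |
| K, moderate | 10 | 7 | 2 |
| K, severe | 10 | 8 | 1 |
| Total | 70 | 38 | 10 |

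All 10 arise through the keratosis/hyperplasia route. Six show new or higher-grade dysplasia (3 + 2 + 1) and four show invasive cancer (one for each baseline state with K). With a no-worsening condition added, 38 − 10 = 28 patterns score yes.

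**Converting to patients.** Section 8.2 says: "The trial will randomize 104 patients (1:1)to receive pembrolizumab versus observation". That is 104 / 2 = 52 per arm. If all 52 are evaluable, one misclassified patient is 1/52 = 1.9 percentage points, two are 3.8 and three are 5.8. With fewer evaluable patients, each one weighs more.

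**Context for the cancer route.** Section 8.2 plans 56 patients with and 48 without prior cancer. An even split gives 28 and 24 per arm. With the plan's exponential hazards and no loss to follow-up, expected cancers by time t (years) are:

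- Observation: 28(1 − e^(−0.1179t)) + 24(1 − e^(−0.0813t)), which is 1.3 at t = 0.25 and 5.0 at t = 1.
- Pembrolizumab: 28(1 − e^(−0.053t)) + 24(1 − e^(−0.0366t)), which is 0.6 at t = 0.25 and 2.3 at t = 1.

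Only cancers seen on a scored biopsy, in a patient whose baseline keratosis or hyperplasia has also gone, would be misclassified. The documents do not say what share that is.

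**The case against.** The strongest objection is that the rule can be read in other ways. It may be keyed to the baseline diagnosis: keratosis or hyperplasia must resolve where that is the diagnosis, and dysplasia must resolve or improve where dysplasia is. The ordered list of histologies in section 4.2.1 lends this some support. On that reading the 3 + 2 + 1 = 6 discordant patterns with baseline dysplasia disappear, but the 4 that start from keratosis or hyperplasia alone remain. If resolution also means return to normal epithelium, all 10 disappear. The documents state neither reading, and in an open-label trial the choice should not wait until results are known. So the objection limits the claim to the literal wording but does not remove the need to settle it.

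It is also fair that the cancer route is narrow. Under section 5.8.1, patients who develop oral cancer have only long-term follow-up procedures afterwards, so a cancer found before month 12 leaves no scheduled month 12 biopsy to score. The overlap is confined to cancer on the month 3 or month 12 biopsy itself.

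Three stronger inferences are tempting, but the documents do not support them:

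- A reader might infer that improvement at one site would hide carcinoma at another. The documents give biopsy times but not the number of sites or which one governs, and they leave collection details to a separate manual.
- A reader might put a figure on the overstatement, such as 2 to 8 points. Any such range only restates an assumed frequency.
- A reader might infer a bias in favor of pembrolizumab. The same rule applies to both arms, and the effect on their difference depends on how often the pattern occurs in each.

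**Conclusion.** The point holds for the rule as written. Loss of baseline keratosis or hyperplasia is sufficient for a response whatever the dysplasia grade, and even with invasive cancer on the same biopsy. No other section overrides this. The clinical scale beside it does define progression, and the biopsies being scored are meant to detect progression, so the gap is foreseeable.

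The error runs one way within each arm, since it can only raise the rate. Its size in patients is unknown; 1.9 points per misclassified patient assumes that all 52 in the arm are evaluable. The count of 10 in 38 describes possible patterns and is not an error rate. The consequence is limited to the secondary histologic response rate and its association with oral cancer-free survival. The primary endpoint, sample size and stopping boundaries are unaffected. The definition should be corrected, but the point does not threaten the trial's main conclusion.

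**What to change.** In section 10.4, define a histologic response as at least one of the improvements already listed, **and** no new or higher-grade dysplasia compared with baseline, **and** no invasive cancer on the study biopsy at that time point. Everything else stays non-response. This settles the competing readings for every pattern that is worse than baseline.

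The change should go no further. Scoring patients with baseline dysplasia on dysplasia grade alone would also reclassify 3 patterns in which keratosis resolves and dysplasia is unchanged, taking the yes patterns from 28 to 25. Those patients have not progressed, so that would be a different endpoint and not a repair of this one.

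The cost is one sentence in the appendix, with no extra biopsy or reading. The reported response rate may be slightly lower.

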10.5 Events of Clinical Interest Guidance Document

Please refer to separate manual provided for biospecimen collection and handling.

10.6 Biospecimen Collection and Handling Guidelines

Please refer to separate manual provided for biospecimen collection and handling.

10.7 Pharmacy Manual

Please refer to separate manual provided for biospecimen collection and handling.

Document Product: JMK-3475, 2016 Protocol/Amendment No.: NCT02882282

